APPENDIX B INVESTIGATOR CONSENT TO USE OF PERSONAL INFORMATION

The sponsor will collect and retain personal information of the investigator, including his or her name, address, and other personally identifiable information. In addition, investigator's personal information may be transferred to other parties located in countries throughout the world (e.g., the United Kingdom, United States, and Japan), including the following:

- The sponsor, its affiliates, and licensing partners.
- Business partners assisting the sponsor, its affiliates, and licensing partners.
- Regulatory agencies and other health authorities.
- IRBs.

The investigator's personal information may be retained, processed, and transferred by the sponsor and these other parties for research purposes including the following:

- Assessment of the suitability of investigator for the trial and/or other clinical trials.
- Management, monitoring, inspection, and audit of the trial.
- Analysis, review, and verification of the trial results.
- Safety reporting and pharmacovigilance relating to the trial.
- Preparation and submission of regulatory filings, correspondence, and communications to regulatory agencies relating to the trial.
- Preparation and submission of regulatory filings, correspondence, and communications to regulatory agencies relating to other vaccines used in other clinical trials that may contain the same chemical compound present in the investigational vaccine.
- Inspections and investigations by regulatory authorities relating to the trial.
- Self-inspection and internal audit within the sponsor, its affiliates, and licensing partners.
- Archiving and audit of trial records.
- Posting investigator site contact information, trial details and results on publicly accessible clinical trial registries, databases, and websites.

Investigator's personal information may be transferred to other countries that do not have data protection laws that offer the same level of protection as data protection laws in the investigator's own country. The investigator acknowledges and consents to the use of his or her personal information by the sponsor and other parties for the purposes described above.

Eff

## 2 Abbreviations and Definitions

ADaM	Analysis Dataset Model
AE	Adverse Event
BMI	Body Mass Index
CI	Confidence Interval
CRF	Case Report Form
CSR	Clinical Study Report
DP	Decimal Place
GI/GII	Genogroup I/ Genogroup II
GI.1/GII.4	Genotype I.1/ Genotype II.4
GII.4c	GII.4 consensus
GM	Geometric Mean
GMT	Geometric Mean Titer
GMFR	Geometric Mean Fold Rise
GSD	Geometric Standard Deviation
HBGA	Histo-Blood Group Antigen
ICH	International Council for Harmonisation of Technical Requirements for Pharmaceuticals for Human Use
IMP	Investigational Medical Product
LLOD	Lower Limit of Detection
LLOQ	Lower Limit of Quantification
MEDRA	Medical Dictionary for Regulatory Activities
pan Ig	Total Immunoglobulin
PT	Preferred Term
SAE	Serious Adverse Event
SAP	Statistical Analysis Plan
SDTM	Standard Data Tabulation Model
SOC	System Organ Class
SRR	Seroresponse Rate
TFL	Tables, Figures and Listings
ULOQ	Upper Limit of Quantification
VLP	Virus-Like Particle
WHODD	World Health Organization Drug Dictionary

### **3 Introduction**

The purpose of this statistical analysis plan (SAP) is to provide all information that is necessary to perform the required statistical analyses of study NOR-215. It also defines the summary tables, figures and listings (TFLs) to be included in the final clinical study report (CSR) according to the protocol. The SAP is based upon, and assumes familiarity, with the study protocol, version 3.0, dated 25OCT2023.

If a future protocol amendment necessitates a substantial change to the statistical analysis of the study data, this SAP will be amended accordingly. The content of this SAP is compatible with the ICH E9 Guidance document.

### **4 Study Objectives and Endpoints**

#### **4.1 Study Objectives**

##### **Primary Objective:**

- To assess the immunogenicity of HIL-214 in serum samples that will form a proficiency panel for further analysis.

##### **Secondary Objective:**

- To assess the safety of HIL-214.

##### **Exploratory Objectives:**

- [REDACTED]
- [REDACTED]

Exploratory objectives and endpoints will not be outlined in this SAP and instead will be documented separately.

#### **4.2 Study Endpoints**

##### **Primary Endpoints:**

At Day 1 and Day 29, (i) histo-blood group antigen (HBGA)-blocking titers and (ii) total immunoglobulin (pan-Ig) titers that are specific for:

- GII.1 virus-like particles (VLP).
- GII.4c VLP.

##### **Secondary Endpoints:**

- Solicited local adverse events (AEs) up to 7 days after the dose of trial vaccine.
- Solicited systemic AEs up to 7 days after the dose of trial vaccine.
- Unsolicited AEs for up to 28 days after the dose of trial vaccine.

- AEs leading to the subject's withdrawal from the trial from Day 1 to the end of the trial.
- Serious adverse events (SAEs) from Day 1 to the end of the trial.

#### Exploratory Endpoints:

- [REDACTED]

## 5 Study Methods

### 5.1 General Study Design and Plan

[figure not shown]
This is a phase 2, single-arm, open-label trial for serologic assay validation, proficiency testing, safety and immunogenicity of HIL-214, in healthy adults aged 18 to 49 years. Vaccination with a single dose of HIL-214 will occur on Day 1.

As shown in **Figure 1**, the study comprises of 3 scheduled site visits (Day 1, Day 8, and Day 29) and one telephone contact (Day 85). Visits 1, 2, and 3 involve blood draws. **Table 1** shows the visit windows for Visits 2 and 3.

The final contact to collect safety data is scheduled on Day 85.

Throughout this document, trial vaccine will refer to the investigational vaccine administration of HIL-214.

**Figure 1: Trial Design Diagram**

**Table 1: Visit Windows**

Day	Day 8	Day 29
Visit window	+2 days	+3 days

### 5.2 Randomization and Blinding

This is a single arm, open-label study with no randomization or blinding.

### 5.3 Derived variables

#### 5.3.1 General

### **5.3.1.1 Baseline**

Unless otherwise stated, baseline is defined as the last non-missing pre-trial vaccine assessment prior to the administration of the trial vaccine.

### **5.3.1.2 Relative Day**

The relative day of an assessment will be calculated as:

- For measurements performed on or after the date of the trial vaccine dose:  
Date of assessment – date of trial vaccine dose+1.
- For measurements performed before the date of the trial vaccine dose:  
Date of assessment – date of trial vaccine dose.

### **5.3.1.3 Demographic and Background Data**

Age will be calculated in years and will be calculated as follows:

$$\text{Age (years)} = (\text{Visit 1 Date (Day 1)} - \text{Date of Birth})/365.25 \text{ [Rounded down to the integer].}$$

Weight may be recorded in kilograms or pounds. Weight in pounds will be converted to weight in kilograms as follows:

$$\text{Weight (kg)} = \text{Weight (lb)} * 0.4536.$$

Weight will be presented to 1 dp in the listings.

Height may be recorded in centimetres or inches. Height in inches will be converted to height in centimetres as follows:

$$\text{Height (cm)} = \text{Height (inches)} * 2.54.$$

Height will be presented to 1 dp in the listings.

Body mass index (BMI) will be calculated as follows:

$$\text{BMI (kg/m}^2\text{)} = \text{Weight (kg)} / (\text{Height (m)}^2).$$

BMI will be present to 1dp in the listings.

Temperature may be recorded in Degrees Celsius or Fahrenheit. Temperature in Fahrenheit will be converted to temperature in Degrees Celsius as follows:

$$\text{Temperature (}^{\circ}\text{C)} = (\text{Temperature (}^{\circ}\text{F)} - 32) * 0.5556.$$

Temperature will be presented to 1 dp in the listings.

## **5.3.2 Immunogenicity**

### **5.3.2.1 Fold Increase**

The fold increase is calculated by taking the ratio of assessments from two visits, which for this study will be Visit 1 (Day 1) and Visit 3 (Day 29) assessments.

If  $v_1$  is a subject's Visit 1 record and  $v_3$  is a subject's Visit 3 record then the fold increase is:

$$fi = \frac{v_3}{v_1}.$$

### 5.3.2.2 Seroresponse Rate

Seroresponse is defined as a fold increase from baseline (Visit 1) greater than or equal to 4.

Seroresponse rate (SRR) is defined as the percentage of subjects with a seroresponse. The 95% confidence intervals (CIs) for the SRR will be computed using the exact Clopper-Pearson method.

### 5.3.2.3 Immunogenicity Assessments

When summarizing immunogenicity assessments the following rules will apply:

- If a record is below the lower limit of detection (LLOD) then ½ the LLOD value will be used in the summary.
- If a record is below the lower limit of quantification (LLOQ) then the midpoint of the LLOQ value and the LLOD value will be used in the summary.
- If a record is above the upper limit of quantification (ULOQ) then the ULOQ will be used in the summary.

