## 5.4 Statistical Analysis Methods

### 5.4.1 Geometric Mean

The geometric mean (GM) of a set of numbers  $x_1, x_2, \dots, x_N$  is calculated by taking the exponential of the mean of the logged values, as per the following formula:

$$GM_x = \exp \left\{ \frac{\sum_{i=1}^N \ln(x_i)}{N} \right\}.$$

The geometric standard deviation (GSD) for the same set of numbers is given by

$$GSD_x = \exp \left\{ \sqrt{\frac{\sum_{i=1}^n \left( \ln \left( \frac{x_i}{GM_x} \right) \right)^2}{n}} \right\}.$$

The 95% confidence interval (CI) is calculated as per the following formula:

$$95\% CI = \exp \left\{ \ln(GM) \pm Z_{1-\frac{\alpha}{2}} \frac{\ln(GSD)}{\sqrt{n}} \right\}$$

where  $\alpha$  is the selected level of confidence. All confidence intervals outlined in this SAP will be two sided 95% confidence intervals, i.e. with  $\alpha = 0.05$ .

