#### 5.4.2 Geometric Mean Fold Rise

The geometric mean fold rise (GMFR) is given by taking the mean of the natural logarithm of the fold increases (Section 5.3.2.2). Therefore, for the fold increases  $fi_1, \dots, fi_n$ , the GMFR is

$$GMFR = \exp \sum_{j=1}^n (\ln\{fi_j\}/n).$$

Which is equivalent to

$$GMFR = \frac{GM_3}{GM_1}$$

where  $GM_1$  is the geometric mean at Visit 1 and  $GM_3$  is the geometric mean at Visit 3.

The 95% confidence interval for GMFR will be calculated using the same method as the 95% CI for GM (outlined in Section 5.4.1) but using the log of the fold rises rather than the log of concentrations.

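### Setting titers above the ULOQ to the ULOQ lowers the Day 29 GMT and overstates its precision if any titers are capped; the effect on GMFR and SRR is conditional, and no censored-data analysis is planned

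*SAP*

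**What the plan says.** SAP 5.3.2.3 gives three substitution rules for out-of-range titers:

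- Above the ULOQ: "If a record is above the upper limit of quantification (ULOQ) then the ULOQ will be used in the summary".
- Below the LLOQ: "then the midpoint of the LLOQ value and the LLOD value will be used in the summary".
- Below the LLOD: "If a record is below the lower limit of detection (LLOD) then ½ the LLOD value will be used in the summary".

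The primary statistics are built on these values. On the fold increase, SAP 5.3.2.1 states: "The fold increase is calculated by taking the ratio of assessments from two visits", here Day 29 over Day 1. On seroresponse, SAP 5.3.2.2 states: "Seroresponse is defined as a fold increase from baseline (Visit 1) greater than or equal to 4". The SRR interval "will be computed using the exact Clopper-Pearson method". SAP 5.4.1 takes the GMT interval from the GSD of the log titers. SAP 5.4.2 uses the same method for the GMFR, "but using the log of the fold rises rather than the log of concentrations".

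SAP 9.1 also tabulates the number of results below the LLOD and LLOQ and above the ULOQ, gives the median and quartiles, and plots a distribution curve for each variable. SAP 9 lists the data by subject. Neither document gives a value for any assay limit, a rule for re-diluting samples above the ULOQ, or a censored-data or sensitivity analysis.

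**The concern.** A titer above the ULOQ is known only to be at least the ULOQ. The rule treats it as exactly the ULOQ. The error goes one way, and it falls mainly on Day 29, where a working vaccine puts the high titers. The capped values also sit at a single point, so the spread of the log titers is understated.

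GMT, GMFR and SRR are the primary analysis (Protocol 13.1.3). Protocol 6.2 intends these titers as positive-control benchmarks and for comparison with other HIL-214 trials. A benchmark with a one-sided error that depends on how many samples ran off the top of the assay is hard to compare with one that has a different share capped.

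**Working it through.** **Inputs.** From the SAP: the three substitution rules, fold = Day 29/Day 1, seroresponse at a fold of 4 or more, z-based 95% CIs on the log scale, Clopper-Pearson for the SRR, n=80. The plan has no figure of its own to reproduce, since the sample size rests on serum volume. Assumed, because the documents are silent: log-normal titers, log10 SD 0.4 to 0.6, and 5, 10 or 20% of Day 29 titers above the ULOQ. I also assume that substituted values enter the fold increase. The rules say only that they are used in the summary, but no other value is given.

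**1. GMT bias.** Let p be the share capped and c the standard normal cut-off with upper tail p. The capped variable min(Z, c) has mean m = −φ(c) + c·p and SD s below 1. Reported/true GMT = 10^(SD × m).

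| p | c | m | s | GMT ratio, SD 0.4 / 0.5 / 0.6 |
|---|---|---|---|---|
| 5% | 1.645 | −0.1031 + 0.0822 = −0.021 | 0.957 | 0.981 / 0.976 / 0.972 |
| 10% | 1.282 | −0.1755 + 0.1282 = −0.047 | 0.915 | 0.957 / 0.947 / 0.937 |
| 20% | 0.842 | −0.2800 + 0.1683 = −0.112 | 0.833 | 0.902 / 0.879 / 0.857 |

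The GMT is therefore low by about 2-3%, 4-6% and 10-14%.

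**2. GMT interval.** Capping cannot move two values further apart, so the sample SD cannot rise. The CI shrinks by about 4%, 9% and 17% (1 − s). Bias and width both scale with the titer SD, so coverage depends only on p and n. Approximately, coverage = Φ(1.96 − δ) − Φ(−1.96 − δ), with δ = |m|√80/s:

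- 5%: δ = 0.20, coverage 95%
- 10%: δ = 0.46, coverage 93%
- 20%: δ = 1.20, coverage 78%

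Simulating the SAP's own formula at n=80 gives about 94%, 93% and 79%. At 5% capped the loss is negligible. At 20% it is not.

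**3. GMFR.** Reported GMFR = true GMFR × (Day 29 ratio)/(Day 1 ratio), so it falls when Day 29 is capped more than Day 1. With SD 0.5 and almost no capping at Day 1, a true 10 becomes 9.8, 9.5 and 8.8. The log half-width of its CI depends on the Day 1/Day 29 correlation (simulated, n=80):

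| Correlation | Uncapped | 5% | 10% | 20% | 40% |
|---|---|---|---|---|---|
| 0.5 | 0.252 | 0.248 | 0.244 | 0.238 | 0.230 |
| 0.8 | 0.159 | 0.158 | 0.158 | 0.161 | 0.172 |

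**4. SRR.** If baseline exceeds ULOQ/4 and Day 29 is at most the ULOQ after substitution, the fold is below 4 whatever the true rise. If every baseline is at or below ULOQ/4, a capped Day 29 titer still gives a fold of at least 4 and the SRR does not change. Simulated, SD 0.5:

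| True GMFR, correlation | True SRR | 5% | 10% | 20% |
|---|---|---|---|---|
| 10, 0.5 | 78.8% | 78.6% | 78.2% | 76.8% |
| 10, 0.8 | 89.6% | 89.1% | 88.3% | 85.8% |
| 5, 0.5 | 57.7% | 57.3% | 56.4% | 53.9% |
| 5, 0.8 | 62.0% | 60.9% | 59.4% | 55.7% |

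The loss is larger when the rise is smaller, because more baselines then lie above ULOQ/4. At correlation 0.5 and 20% capped, 5.1% do so for a true GMFR of 10, and 15.1% for a true GMFR of 5. The Clopper-Pearson width depends only on the count: 72/80 has width 0.143 and 64/80 has 0.186, so losing responders above 50% widens the interval.

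**5. Low end.** Day 1 below the LLOD and Day 29 between LLOD and LLOQ gives a fold of [(LLOD + LLOQ)/2]/(LLOD/2) = 1 + LLOQ/LLOD. That is 3, 4 and 5 for LLOQ/LLOD of 2, 3 and 4. Two unquantified titers count as a seroresponse only if LLOQ is at least 3 times LLOD. Simulated effects on the SRR were about 1 point or less; one subject in 80 is 1.25 points.

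**6. Does the alternative work?** A right-censored log-normal likelihood fitted to the same capped data at n=80 gave GMT ratios of 1.00 at 5, 10 and 20% capped.

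**The case against.** The best defence is that nothing in the documents shows any titer will exceed the ULOQ. If none does, the high-end rule does nothing. The analysis is descriptive, with no hypothesis test. At 10% capped and SD 0.5, a GMT about 5% low is small beside a CI that reaches a factor of exp(0.252) = 1.29 either way. SAP 9.1 makes the censoring visible: the median is unaffected while fewer than half the titers are capped, and the upper quartile while fewer than a quarter are. Simple substitution may also be what the other HIL-214 trials used, though the documents do not say.

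Most of this stands, and it limits the point. It does not remove it. Counts and quartiles tell the reader that the GMT is biased, but they do not correct the GMT, the GMFR or their intervals. Comparability is a reason to keep the substitution analysis, not to have it alone.

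A reader might also infer that the rule narrows all three intervals. The documents do not support that: the SRR interval is exact binomial and does not involve the GSD, and the GMFR interval can go either way. Nor does the SRR always fall; that needs true responders with baselines above ULOQ/4.

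**Conclusion.** The point holds in conditional form. If any Day 29 titers exceed the ULOQ, the Day 29 GMT is biased down with too narrow a CI. The GMFR is biased down when Day 29 is capped more than Day 1, and the SRR can fall but cannot rise through the ULOQ rule. The effect is slight at 5% capped and material for the GMT at 20%.

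These sizes rest on log-normal titers, the assumed SDs, correlations and shares capped, and on substituted values entering the fold increase. The true shares cannot be derived from the documents.

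The low-end artefact is a minor matter. A reader might take it as a second source of material bias, but it needs an LLOQ/LLOD ratio that the documents do not give, and its simulated effect is small.

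**What to change.** Keep the substitution analysis, for comparison with other trials. In SAP 5.3.2.3 and 5.4, state the assay limits and that substituted values enter the fold increase. Then pre-specify that, if any titers are out of range:

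1. GMT and GMFR with CIs are also estimated by maximum likelihood for censored log titers (left, interval and right censored). For the GMFR use a bivariate Day 1/Day 29 model, or one that allows for baseline, because the censoring point of the fold is ULOQ/baseline and differs between subjects.
2. SRR is also given with subjects who have baseline above ULOQ/4 and Day 29 above the ULOQ counted all as responders, and then all as non-responders.
3. As a sensitivity analysis only, and only if LLOQ is at least 3 times LLOD, SRR is also reported without seroresponses whose Day 29 titer is below the LLOQ. This should not become part of the definition, since Protocol 13.1.3 defines seroresponse by the 4-fold rise alone.

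The cost is SAP text and some extra programming: standard code for the GMT, somewhat more for the GMFR model. The downside is a second set of estimates, which rest on a log-normal assumption. Deciding this before the share above the ULOQ is known avoids a post-hoc choice.

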## 5.4 Statistical Analysis Methods

### 5.4.1 Geometric Mean

The geometric mean (GM) of a set of numbers  $x_1, x_2, \dots, x_N$  is calculated by taking the exponential of the mean of the logged values, as per the following formula:

$$GM_x = \exp \left\{ \frac{\sum_{i=1}^N \ln(x_i)}{N} \right\}.$$

The geometric standard deviation (GSD) for the same set of numbers is given by

$$GSD_x = \exp \left\{ \sqrt{\frac{\sum_{i=1}^n \left( \ln \left( \frac{x_i}{GM_x} \right) \right)^2}{n}} \right\}.$$

The 95% confidence interval (CI) is calculated as per the following formula:

$$95\% CI = \exp \left\{ \ln(GM) \pm Z_{1-\frac{\alpha}{2}} \frac{\ln(GSD)}{\sqrt{n}} \right\}$$

where  $\alpha$  is the selected level of confidence. All confidence intervals outlined in this SAP will be two sided 95% confidence intervals, i.e. with  $\alpha = 0.05$ .

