13.1.3 Primary Analysis - Immunogenicity

Descriptive statistics will be computed for HBGA-blocking titers and pan-Ig titers against GI.1 and GII.4c, measured at Day 1 and Day 29. These statistics will include the geometric mean titers (GMTs), geometric mean fold rise in titers (GMFR) from baseline (Day 1), and seroresponse rate (SRR). The SRR is defined as the percentage of subjects with a seroresponse, where seroresponse is a ≥ 4 -fold rise in titer from baseline (Day 1). The 95% confidence intervals (CI) will be provided for geometric means and the SRRs.

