## 6 Sample Size

A sample size of 80 subjects will provide sufficient serum for the establishment of proficiency panels to confirm assay validation of the validated serology assays planned to support the clinical development plan for HIL-214.

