## **9 Immunogenicity Analysis**

The primary endpoint will consider the immunogenicity of HIL-214 at Visit 3 (Day 29) and all analysis will be defined in this section. Analyses will be completed for the safety analysis set and per protocol analysis set. Subjects with immunogenicity samples taken outside of the visit windows (as described in **Table 1**) will not be included in analyses which use the per protocol analysis set.

The immunogenicity variables, HBGA-blocking titers and total immunoglobulin (pan-Ig) titers that are specific for GI.1 VLP and GII.4c VLP will be summarized. Along with the following summaries, the immunogenicity data will be listed by subject.

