### **9.1 Main Analytical Approach**

For all immunogenicity variables a standard summary of the number of subjects with an assessment (n), mean, standard deviation, median, Q1, Q3, minimum and maximum will be presented alongside the number of assessments below the LLOQ and LLOD and above the ULOQ. The number of subjects that are missing an assessment will also be summarized.

As well as the standard continuous summary of the outcomes, geometric mean titers (GMTs), geometric mean fold rise (GMFR) and seroresponse rate (SRR) will be presented (as defined in **Sections 5.3.2 and 5.4**) for each immunogenicity variable. The 95% confidence intervals (CI) for GM, GMFR and SRR as well as geometric standard deviation (GSD) will also be provided.

In addition, for each immunogenicity variable a reverse cumulative distribution curve will be produced, with titer on the x-axis and the percentage of subjects below the titer value on the y-axis.

Line graphs and boxplots summarizing the GMT for each trial vaccine group for the serotypes GI.1 and GII.4 will also be produced. These outputs will both have the visits of baseline (Day 1) and Visit 3 (Day 29) on the x-axis and the GMT on the y-axis, presenting data on the log scale.

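### The GMT and GMFR 95% intervals use a divide-by-n log SD and a normal quantile, so at n = 80 they cover about 94.5% for normal log titers

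*SAP*

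**What the plan says.** SAP 5.4.1 first defines the spread: "The geometric standard deviation (GSD) for the same set of numbers is given by" the exponential of the root of the summed squared log deviations divided by n. It then states "The 95% confidence interval (CI) is calculated as per the following formula": exp{ln(GM) ± Z(1−α/2) × ln(GSD)/√n}, with α = 0.05. The level is explicit: "All confidence intervals outlined in this SAP will be two sided 95% confidence intervals".

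SAP 5.4.2 carries this over: "The 95% confidence interval for GMFR will be calculated using the same method as the 95% CI for GM", working on log fold rises. SAP 9.1 lists what is reported: "The 95% confidence intervals (CI) for GM, GMFR and SRR as well as geometric standard deviation (GSD) will also be provided". SAP 9 adds: "Analyses will be completed for the safety analysis set and per protocol analysis set".

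Protocol 13.1.3 places these intervals in the primary analysis without giving a formula: "The 95% confidence intervals (CI) will be provided for geometric means and the SRRs". Neither document specifies a t quantile or an n−1 divisor for them.

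**The concern.** The formula treats the log SD as known, but it is estimated from the same titers. Two features push the same way. Divisor n makes the SD estimate smaller than the usual n−1 estimate, and the normal quantile is smaller than the t quantile that allows for the SD being estimated. Both narrow the interval, so it falls short of its 95% label when logs are normal. The GSD is reported in its own right, so the divisor also affects that statistic.

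The intervals concerned are those for 4 variables (2 assays × 2 antigens), each with a GMT at 2 visits and one GMFR: 4 × 3 = 12 per analysis set, or 24 over the two sets. Protocol 13.1.1 makes the per-protocol results supportive, so 12 of the 24 belong to the main analysis. The seroresponse interval is unaffected, because SAP 5.3.2.2 uses the exact Clopper-Pearson method.

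**Working it through.** **Inputs.** α = 0.05, two-sided (SAP 5.4.1). n = 80 planned (SAP 6: "A sample size of 80 subjects will provide sufficient serum"). Z(0.975) = 1.95996. The log SD is not given, but for normal logs coverage depends only on n. The numbers of evaluable and per-protocol subjects are not given either; 60 to 80 is assumed as a range.

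**Coverage.** Let s be the log SD with divisor n−1. For normal logs, (mean − μ)/(s/√n) follows t with n−1 degrees of freedom. The SAP's ln(GSD) equals s√((n−1)/n), so the SAP interval is mean ± c·s/√n with c = Z√((n−1)/n), and its coverage is P(|T| < c) for T on n−1 degrees of freedom.

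The plan's own figure is 95%. At n = 80 it is not reproduced:
- c = 1.95996 × √(79/80) = 1.9477
- t(0.975, 79) = 1.9905
- width ratio = 1.9477/1.9905 = 0.9785, so 2.15% too narrow on the log scale
- split: Z/t = 0.9847 (1.53% narrower) and √(79/80) = 0.9937 (0.63% narrower)
- coverage = P(|T79| < 1.9477) = 94.50%

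A simulation of 400,000 normal samples of size 80 gave 94.49%.

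Changing one element at a time, n = 80:

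| Quantile | Divisor | Coverage |
|---|---|---|
| Z | n (SAP) | 94.50% |
| Z | n−1 | 94.65% |
| t | n | 94.86% |
| t | n−1 | 95.00% |

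SAP formula at smaller assumed n:

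| n | Coverage | Too narrow (log scale) |
|---|---|---|
| 72 | 94.44% | 2.39% |
| 64 | 94.37% | 2.69% |
| 60 | 94.33% | 2.87% |

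**Titer scale, n = 80.** With log SD s assumed at 0.5 to 1.5, the limits are GM × exp(∓1.9477·s/√80) under the SAP and GM × exp(∓1.9905·s/√80) with t and n−1. The GSD is exp(s√(79/80)) against exp(s).

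| Assumed s | SAP limits (× GM) | t, n−1 limits (× GM) | SAP GSD | n−1 GSD | GSD lower by |
|---|---|---|---|---|---|
| 0.5 | 0.897 to 1.115 | 0.895 to 1.118 | 1.644 | 1.649 | 0.31% |
| 1.0 | 0.804 to 1.243 | 0.800 to 1.249 | 2.701 | 2.718 | 0.63% |
| 1.5 | 0.721 to 1.386 | 0.716 to 1.396 | 4.440 | 4.482 | 0.94% |

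**The case against.** The strongest reply is that this is a choice of method. The SAP openly prespecifies a recognised large-sample interval that anyone can reproduce, the protocol names no method, and divisor n is a legitimate stated definition of a descriptive GSD. No conclusion changes: the sample size rests on serum supply, and there is no hypothesis, threshold or precision target. This stands as to weight, and for the GSD taken alone the divisor is a matter of convention. It does not remove the mismatch between the interval's 95% label and what the formula delivers.

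A second reply is that actual coverage is not known to be 94.5%. SAP 5.3.2.3 substitutes values below the detection and quantification limits and caps those above the upper limit, so the analysed logs need not be normal, and coverage could move either way. Nor does the t interval then guarantee 95%. In an illustrative simulation with assumed inputs (n = 80, normal logs, values below the detection limit set to half of it), the t interval with n−1 covered the true log mean 94.2% of the time with log SD 1.0 and 20% of values below the limit, and 92.7% with log SD 1.5 and 30% below. This is correct, and it is why the 94.50% is stated for normal logs. Substitution is a separate source of error, however. In such simulations the t interval with n−1 still covered about 0.5 to 0.7 percentage points better than the SAP formula.

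Third, Protocol 6.2 uses these titers for comparison with other HIL-214 trials. Whether those trials use the same interval formula cannot be seen from the documents, so the effect on comparability is unknown.

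**Conclusion.** The point holds and is minor. For normal log titers at the planned n = 80, the GMT and GMFR intervals labelled 95% cover 94.50% and are 2.15% too narrow on the log scale. At an assumed n of 60 the figures are 94.33% and 2.87%. These figures rest on normal logs. With substituted or capped titers the actual coverage may differ. The reported GSD is 0.31% to 0.94% lower than its n−1 counterpart for assumed log SDs of 0.5 to 1.5. The analysis is descriptive and no decision depends on these intervals, so this is a correction worth considering rather than one the trial needs in order to be interpretable.

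**What to change.** In SAP 5.4.1, divide by n−1 in the GSD and replace Z(1−α/2) with t(0.975, n−1), where n is the number of subjects contributing to that estimate. SAP 5.4.2 then inherits the change for the GMFR. For normal logs this gives exactly 95%.

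The cost is a wording change in the SAP, plus updating and checking the affected outputs. No protocol amendment is needed, since Protocol 13.1.3 gives no formula. Intervals widen by 1.9905/1.9477 − 1 = 2.20% on the log scale at n = 80, and by 2.96% at an assumed n = 60. If results are set beside those of other HIL-214 trials, the report should state which formula each uses.

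Two optional wording corrections could be made in SAP 5.4.2 at the same time; neither affects coverage. The GMFR and its interval are correctly defined from within-subject fold rises, but the added identity GMFR = GM3/GM1 should be limited to subjects with titers on both Day 1 and Day 29. The reference for the fold increase should point to 5.3.2.1 instead of 5.3.2.2.
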